#### 10.6.4 Secondary Efficacy Analyses

Change from baseline in ETDRS BCVA letters to Weeks 2, 4, 8, and 16 and ETDRS BCVA letters at Weeks 2, 4, 8, 12, and 16 will be analyzed similarly to the primary efficacy analyses using ODO on the ITT population.

Mean and mean change in central retinal subfield thickness will be analyzed similarly to ETDRS BCVA.

The proportion of study eyes a) gaining at least 10 or 15 letters BCVA and b) losing at least 15 letters will be summarized using discrete summary statistics. Treatment comparisons will be completed using Pearson's chi-squared statistic, with Fisher's exact statistic used for any comparison with an expected cell frequency of 5 or less. Confidence intervals (70%, 90%, and 95%) will also be presented for each treatment group and the difference between treatment groups, using asymptotic or exact methodology as consistent with the employed testing procedure. The analyses will be completed primarily on the ITT population and secondarily on the PP populations using ODO.

In all of these analyses, data from subject visits after receipt of rescue medication will be imputed using last observation prior to receiving rescue medication for continuous endpoints and will be imputed as failures for success/failure variables.

The VFQ-25 measurements will be summarized using continuous summary statistics for the total score, subscale scores, and each individual question score using observed data only. Imputation of missing individual question scores in calculating subscale and total scores will be detailed in the formal statistical analysis plan and will follow methodology used in developing the instrument.

One-sample t-tests will be used to primarily analyze the mean change from baseline within a treatment group; additionally, the non-parametric Wilcoxon signed-rank test will be used secondarily to analyze the change from baseline. Two-sample t-tests will be used to primarily analyze the difference in the mean scores between treatments at each visit and change from baseline; additionally, the non-parametric Wilcoxon rank-sum test will be used secondarily to analyze the differences in scores between treatments.

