**Study group.**

The study eye will receive 1 DexNP eye drop 3 times a day (every 8 hrs) for 12 weeks.

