### 8.2 Concurrent Therapies

The use of any concurrent medication, prescription or over-the-counter, is to be recorded on the subject's source document and corresponding case report form (CRF) along with the reason the medication was taken.

Concurrent use of other eye drops is not allowed. Should concurrent treatment with IOP lowering eye drops (prefer prostaglandin) become necessary due to increased IOP, those eye drops should be administered in the evening 15 minutes before DexNP/Vehicle eye drops.

Other treatments for DME are not allowed in the study eye while the patients are included in the study except if they meet the rescue criteria as described in 8.2.2 below.

If the fellow eye needs any treatment for DME or any other conditions, standard of care (i.e. anti-VEGF for DME) can be applied except steroids. So i.e. Ozurdex or topical dexamethasone will not be allowed for the treatment of the fellow eye during the course of the study.

The use of contact lenses is NOT allowed during the active study treatment phase of 12 weeks.

Concurrent enrollment in another investigational drug or medical device study is not permitted.

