#### 10.1.2 Secondary Efficacy Endpoints

- Mean change in ETDRS BCVA letters at Weeks 2, 4, 8, and 16 compared to baseline
- Mean ETDRS BCVA letters at Weeks 2, 4, 8, 12, and 16
- Proportion of subjects with  $\geq 10$  and  $\geq 15$  ETDRS BCVA letter improvements from baseline.
- Proportion of subjects reaching 20/20 vision at week 12
- Proportion of subjects with  $\geq 15$  ETDRS BCVA letter loss from baseline.
- Mean change in central macular thickness (CMT) as assessed by SD-OCT at Weeks 2, 4, 8, 12, and 16 compared to baseline
- Mean CMT as assessed by SD-OCT at Weeks 2, 4, 8, 12, and 16
- Quality of life as assessed at week 12 by NEI VFQ-25

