#### PART 1 - GENERAL HEALTH AND VISION

1. In general, would you say your overall health is\*:

(Circle One)

READ CATEGORIES:	
Excellent	1
Very Good	2
Good	3
Fair	4
Poor	5

2. At the present time, would you say your eyesight using both eyes (with glasses or contact lenses, if you wear them) is excellent, good, fair, poor, or very poor or are you completely blind?

(Circle One)

READ CATEGORIES:	
Excellent	1
Good	2
Fair	3
Poor	4
Very Poor	5
Completely Blind	6

\* Skip Question 1 when the VFQ-25 is administered at the same time as the SF-36 or RAND 36-Item Health Survey 1.0

3. How much of the time do you worry about your eyesight?

(Circle One)

READ CATEGORIES:

- |                           |   |
|---------------------------|---|
| None of the time.....     | 1 |
| A little of the time..... | 2 |
| Some of the time.....     | 3 |
| Most of the time .....    | 4 |
| All of the time?.....     | 5 |

4. How much pain or discomfort have you had in and around your eyes (for example, burning, itching, or aching)? Would you say it is:

(Circle One)

READ CATEGORIES:

- |                 |   |
|-----------------|---|
| None.....       | 1 |
| Mild.....       | 2 |
| Moderate.....   | 3 |
| Severe, or..... | 4 |

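### The VFQ-25 measures two-eyed function while one eye is treated, yet section 10.6.4 makes no use of the fellow eye: the between-arm test stays valid but may be diluted and noisy, and the within-arm tests are unprotected

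*Combined protocol and SAP*

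**What the plan says.** - **Treatment.** Section 7.1.2 doses one eye: "The study eye will receive 1 DexNP eye drop 3 times a day (every 8 hrs) for 12 weeks". The control arm is dosed the same way with vehicle.
- **Eligibility.** The acuity and thickness limits in section 5.3 are set for the study eye. No acuity limit is set for the fellow eye. No rule says which eye becomes the study eye when both qualify, or whether it must be the better- or worse-seeing one.
- **Fellow-eye treatment.** Section 8.2 provides that "standard of care (i.e. anti-VEGF for DME) can be applied except steroids" in the fellow eye during the study.
- **Instrument.** The endpoint in section 10.1.2 is "Quality of life as assessed at week 12 by NEI VFQ-25". Item 2 of the questionnaire (Appendix 2) begins "At the present time, would you say your eyesight using both eyes". The activity items cover tasks such as reading, stairs and driving, and no item refers to the study eye alone. Appendix 1 schedules the questionnaire at Day 1 and Week 12.
- **Analysis.** Section 10.6.4 states "The VFQ-25 measurements will be summarized using continuous summary statistics for the total score, subscale scores, and each individual question score", on observed data. The paragraph that follows, which I read as governing these scores, makes one-sample t-tests primary within arm. Between arms, "Two-sample t-tests will be used to primarily analyze the difference in the mean scores between treatments at each visit and change from baseline". Wilcoxon tests are secondary. No covariate, stratum or sensitivity analysis involves the fellow eye. Section 10 mentions the fellow eye only for ocular adverse events (10.6.5).
- **Contrast.** The primary BCVA analysis in 10.6.3 is a linear model adjusted for the baseline value.

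**The concern.** The drug acts on one eye and the questionnaire scores the person. If the fellow eye sees well, a gain in the study eye may change daily function little. If the fellow eye is treated between Day 1 and Week 12, the score can move for reasons unrelated to the drops. The planned analysis neither measures nor adjusts for either effect.

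Two interpretations are at stake. A null between-arm VFQ-25 result could mean that the drops bring no functional benefit, or that many study eyes were the worse-seeing eye. The planned tables would not separate these. A nominally significant improvement within an arm could also be credited to the drops when fellow-eye treatment contributed to it. Quality of life is listed as a secondary objective in the synopsis, so both readings are likely to be reported.

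**Working it through.** **1. The plan's own figure.** Section 10.3 gives a 3.5-letter difference, SD 8, one-sided alpha 0.15, 58 DexNP and 29 vehicle, and 80% power.

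- Standardized effect: 3.5/8 = 0.4375.
- √(1/58 + 1/29) = 0.2274, so the noncentrality is 0.4375/0.2274 = 1.924.
- Fixed-design power is 0.81. With the two looks of section 10.4 (boundaries 1.73051 and 1.08968 at 50% information), overall alpha is 0.1500 and power 0.806.

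The stated design reproduces. It concerns study-eye BCVA only. The documents give no effect, SD or power for the VFQ-25.

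**2. What randomization settles.** Baseline fellow-eye acuity, better/worse-eye status and the need for fellow-eye treatment are balanced between arms in expectation under masked 2:1 allocation. What remains is chance imbalance. If a proportion p of fellow eyes is treated (assumed 10% to 40%; no rate is given), the standard error of the arm difference in that proportion is √[p(1−p)(1/58 + 1/29)]:

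- p = 0.10: 0.300 × 0.2274 = 0.068
- p = 0.40: 0.490 × 0.2274 = 0.111

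That is 7 to 11 percentage points of noise around zero, which the two-sample standard error already covers. It is not systematic bias.

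**3. How much of a study-eye gain might reach two-eyed function.** The documents do not give the fellow-eye distribution, so this is a range on assumptions: study-eye BCVA normal with mean parameter 55 to 65 and SD 12, truncated to the entry range of 24 to 73 letters; fellow-eye BCVA normal with mean 60 to 75 and SD 15; eyes independent.

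- If function follows the better eye, the study eye is the better one in 12% to 50% of patients. A 3.5-letter study-eye gain then raises better-eye acuity by 0.5 to 1.9 letters, a carry-through of 0.5/3.5 = 14% to 1.9/3.5 = 54%.
- If function follows the average of the two eyes, carry-through is 1.75/3.5 = 50%.

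**4. Illustrative effect on power.** Suppose the VFQ-25 would show the BCVA standardized effect if it reflected the study eye alone, and a fraction w carries through. Two-sample t-test, 85 degrees of freedom, one-sided 0.15 (section 10.6.1), noncentrality 1.924 × w:

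| w | standardized effect | power |
|---|---|---|
| 1.00 | 0.438 | 0.81 |
| 0.75 | 0.328 | 0.66 |
| 0.50 | 0.219 | 0.47 |
| 0.25 | 0.109 | 0.29 |

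**5. What baseline adjustment could recover.** At w = 0.5, if the covariates explained a share R² of the variance, the noncentrality becomes 0.962/√(1−R²). Power rises from 0.47 to 0.49 at R² = 0.10 and to 0.63 at R² = 0.50 (both assumed).

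**6. Within-arm tests.** A one-sample test of change attributes to the arm everything that happened between Day 1 and Week 12, including fellow-eye treatment. Randomization does not protect it, because no comparison group enters the test.

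**The case against.** The strongest reply is that the endpoint is patient-level quality of life and the documents nowhere claim that the VFQ-25 isolates a study-eye effect. Using a person-level instrument in a simple randomized comparison is legitimate, and the result answers a real question: what does treating one eye do for the patient? This stands, and it limits the point to precision and interpretation.

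Two stronger readings are tempting, and the documents do not support either.

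- A reader might infer that the VFQ-25 comparison mostly measures something other than the treatment. That is not shown. Low carry-through depends on assuming that function follows the better eye, and even then the range runs from 14% to 54%. Items on worry, eye discomfort and noticing objects to the side need not follow better-eye acuity at all.
- A reader might infer that a between-arm difference could be an artefact of fellow-eye treatment. Under masked randomization such treatment is balanced in expectation, and chance imbalance is part of the test's stated error.

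The reply is also right that main-effect covariates reduce variance without undoing dilution, that dropping patients whose fellow eye was treated would select on a post-randomization event, and that the better-eye stratum is small. At 12% to 50% of 87 it holds about 10 to 44 patients, roughly 3 to 15 of them on vehicle. None of this defends the within-arm tests, or the absence of any information by which to interpret a null result.

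**Conclusion.** The point holds as one of precision and interpretation on a secondary endpoint. The between-arm VFQ-25 test is unbiased for the effect of treating one eye on patient-level quality of life. It may understate a benefit in the study eye, and it carries fellow-eye variation that baseline data could partly remove. The within-arm tests cannot be attributed to the drops.

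The size cannot be computed: the documents give no VFQ-25 effect or SD, no fellow-eye acuity distribution and no fellow-eye treatment rate. The power range of 0.81 down to 0.29 borrows the BCVA effect for a questionnaire that was never powered, and the carry-through range rests on an assumed acuity model. Both show direction and plausible scale only. Trial success depends on Week 12 BCVA alone, so the primary inference and the sample size do not change.

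**What to change.** In section 10.6.4:

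1. Make the primary between-arm VFQ-25 analysis a linear model of the kind used in 10.6.3, with treatment, baseline VFQ-25 score, and either baseline fellow-eye BCVA or an indicator of whether the study eye is the better- or worse-seeing eye. Choose the covariate before unmasking.
2. Present the treatment difference by better/worse-eye status as a pre-specified descriptive subgroup, with intervals. Do not make either stratum the definitive reading.
3. Tabulate fellow-eye DME treatment before Week 12 by arm. Treat it as an intercurrent event in a sensitivity analysis that keeps all randomized patients, for example by setting later scores to missing and multiply imputing them. Do not exclude these patients, and do not adjust for the treatment as a covariate.
4. Label the within-arm t-tests and signed-rank tests descriptive.
5. State that a null pooled VFQ-25 result does not exclude a study-eye benefit.

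In section 8.3.1, state that BCVA is recorded in both eyes at Day 1; the section does not now say so. Also state how the study eye is chosen when both eyes qualify.

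The cost is SAP text, a few tables and possibly one CRF field. The section already defers VFQ-25 item imputation to a formal SAP, so the text has a natural place. The downside is slightly more analysis work and wide intervals in the small strata.

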## 10.6 Statistical Analysis

### 10.6.1 Methods of Analysis

Summaries for continuous variables will include the sample size, mean, standard deviation, median, minimum, and maximum. Summaries for discrete variables will include frequencies and percentages. Differences between treatment groups will be calculated as DexNP – Vehicle and change from baseline will be calculated as follow-up visit – baseline. The baseline visit will be defined as the last non-missing measure prior to initiation of investigational treatment. All efficacy analyses will use a one-sided alpha = 0.15 test unless otherwise stated.

All summaries will be presented by treatment group and where appropriate by visit.

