### 10.6.3 Primary Efficacy Analysis

The primary efficacy variable (change from baseline in ETDRS BCVA letters to Week 12) will be summarized using continuous summary statistics, including 70%, 90% and 95% confidence intervals (CIs) for each treatment group. The primary analysis of the primary variable will employ a linear model with change from baseline ETDRS BCVA letters as the response, baseline ETDRS BCVA letters as a covariate, and treatment as a main effect factor, using the ITT population and with multiple imputation pattern mixture model techniques used to impute missing data. Subjects who receive rescue medication prior to Week 12 will have their Week 12 measure replaced with

their last observation prior to receiving rescue medication. The least squared mean, standard error, and CI for each treatment group, and the difference between treatment groups, will be presented as well as a 1-sided p-value testing the difference versus the null hypothesis value of 0. The study will be considered a success and DexNP superior to Vehicle if the one-sided p-value is less than 0.15 and the difference in mean change from baseline ETDRS BCVA letters is greater than 0. Analyses will secondarily be completed using a two-sample t-test.

The primary efficacy analyses will secondarily be performed on the ITT population using observed data only (ODO), last observation carried forward (LOCF), and baseline observation carried forward (BOCF) to assess the robustness of the results from the primary model. The primary efficacy analyses using multiple imputation and ODO will also secondarily be completed on the PP population. In all of these analyses, subjects who receive rescue medication prior to Week 12 will have their Week 12 measure replaced with their last observation prior to receiving rescue medication.

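### The NEI VFQ-25 is compared between arms by unadjusted t-tests on both score and change, with no baseline covariate and no main comparison named, although BCVA and CMT are analysed with baseline as a covariate.

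*Combined protocol and SAP*

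**What the plan says.** Quality of life is a secondary objective in the Synopsis and a secondary efficacy endpoint in Sections 6.1.2 and 10.1.2. The VFQ-25 is collected at baseline and Week 12 only (Section 8.3.1 and Appendix 1). The endpoint list in 10.1.2 fixes Week 12, but it does not say whether the endpoint is the value or the change, or the total or a subscale.

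Section 10.6.4 plans summaries "for the total score, subscale scores, and each individual question score using observed data only". For the between-arm comparison it says: "Two-sample t-tests will be used to primarily analyze the difference in the mean scores between treatments at each visit and change from baseline". Then "the non-parametric Wilcoxon rank-sum test will be used secondarily to analyze the differences in scores between treatments". The only VFQ-25 matter passed to a later document is item imputation: "Imputation of missing individual question scores in calculating subscale and total scores will be detailed in the formal statistical analysis plan".

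For BCVA, Section 10.6.3 specifies a linear model for change with "baseline ETDRS BCVA letters as a covariate, and treatment as a main effect factor", and adds: "Analyses will secondarily be completed using a two-sample t-test". Section 10.6.4 carries this over to OCT thickness: "Mean and mean change in central retinal subfield thickness will be analyzed similarly to ETDRS BCVA". Section 10.6.1 sets the test level: "All efficacy analyses will use a one-sided alpha = 0.15 test unless otherwise stated".

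**The concern.** The VFQ-25 is the only continuous efficacy endpoint without the baseline-covariate model, and no reason is given. The text ranks the t-test above the Wilcoxon test. It does not rank score against change, or the total above subscales and items. Two things follow.

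- **Precision.** A t-test on the score ignores baseline, and a t-test on change subtracts it in full. With equal SDs, a model that estimates the slope is more precise than either unless the correlation is close to 0 or to 1.
- **An open choice of result.** A chance baseline imbalance moves the two t-tests in opposite directions, so they can lead to different conclusions, and the plan does not say which to read. Adjustment settles this, because with baseline as a covariate the treatment estimate is the same whether the response is score or change.

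**Working it through.** **Plan's own figure.** No sample size is given for the VFQ-25, so the group sizes come from Section 10.3 (58 and 29). These reproduce. With 3.5 letters, SD 8, one-sided 0.15, 2:1 allocation and O'Brien-Fleming-type spending at 50% information, the boundaries are 1.7305 and 1.0897. Power is 80.6% at 58/29 and 79.6% at 56/28.

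**Assumptions.** The documents give no VFQ-25 SD, effect or baseline to Week 12 correlation r. I take equal SDs at both times and in both arms, a common r of 0.3 to 0.9, and a true effect of 0.3 SD.

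**Formulas.** Let f = √(1/58 + 1/29) = 0.2274 and z(0.85) = 1.0364. In units of SD² × f², the variance of the estimated difference is:

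- score t-test: 1
- change t-test: 2(1 − r)
- baseline-adjusted: 1 − r², times about 1 + 1/(87 − 4) = 1.012 for estimating the slope

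Power = Φ(0.3/(f√v) − 1.0364), where v is the variance above.

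Example at r = 0.7:

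- Score: 0.3/0.2274 = 1.319, so Φ(0.283) = 61.1%.
- Change: v = 0.6, 1.319/√0.6 = 1.703, so Φ(0.667) = 74.7%.
- Adjusted: v = 0.51 × 1.012 = 0.516, so 78.8%.

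| r | Score variance ÷ adjusted | Change variance ÷ adjusted | Better t-test ÷ adjusted, net of slope | Power, better t-test | Power, adjusted (net) | Gain, points |
|---|---|---|---|---|---|---|
| 0.3 | 1.10 | 1.54 | 1.09 | 61.1% (score) | 63.2% | 2.1 |
| 0.5 | 1.33 | 1.33 | 1.32 | 61.1% (either) | 68.4% | 7.2 |
| 0.7 | 1.96 | 1.18 | 1.16 | 74.7% (change) | 78.8% | 4.1 |
| 0.8 | 2.78 | 1.11 | 1.10 | 85.3% (change) | 87.5% | 2.2 |
| 0.9 | 5.26 | 1.05 | 1.04 | 97.2% (change) | 97.6% | 0.4 |

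Gains are taken before rounding. The first two ratio columns leave out the slope cost. Without that cost, the gains are 0.5 to 7.5 points.

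**Simulation check.** With actual t-tests and the covariate model, 40,000 trials per setting, adjusted power was 62.9%, 68.3%, 78.7%, 87.5% and 97.5%. Adjusted type I error was 14.7% to 15.2%. One 20,000-trial run gave 16.6% at r = 0.7; two 40,000-trial runs with other seeds did not repeat it (14.9% and 14.8%).

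**Disagreement between the two t-tests.** A baseline imbalance of one standard error is 0.23 SD. At r = 0.7 it shifts the score comparison by 0.7 × 0.2274 = +0.16 SD and the change comparison by (0.7 − 1) × 0.2274 = −0.07 SD. The two z-statistics have correlation √((1 − r)/2), which is 0.59 at r = 0.3 and 0.22 at r = 0.9. With no effect, one test crosses one-sided 0.15 and the other does not in 17%, 18%, 20%, 21% and 23% of trials across the five values of r. With a 0.3 SD effect the range is 30% to 38%.

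**The case against.** The strongest reply is that nothing here is an error. The t-tests are valid, the endpoint is secondary, nothing is powered on it, and different methods for different endpoints are not a contradiction. That is right, and it limits the point to efficiency and clarity.

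The size also needs care. Section 10.6.4 plans both score and change, so the better t-test will always be available. The large ratios for the weaker test, up to 5.26, therefore overstate the loss; at r = 0.9 the change test already has 97.2% power. The fair measure is the net gain over the better t-test, which exceeds 5 points only near r = 0.5. Because the plan does not say which test to read, the weaker one could still be taken as the result.

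The disagreement rates count significance decisions, not opposite signs. Estimates with opposite signs at a 0.3 SD effect occur in about 9% to 14% of trials. The chance that at least one test is positive with no effect (23% to 26%) is illustrative only, since the plan has no either-test rule.

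Two further points carry less weight. The t-test paragraph does not itself name the VFQ-25, but it follows the VFQ-25 paragraph, speaks of scores, and every other secondary efficacy variable that 10.6.4 covers already has its own method. A separate formal analysis plan might name a main comparison, but Section 10.6.4 defers only item imputation to it and prescribes the tests itself.

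**Conclusion.** The concern holds. Section 10.6.4 analyses the VFQ-25 without the baseline covariate that the plan uses for BCVA and CMT, and it names neither a main form (score or change) nor a main score. Net of the slope cost, the better planned t-test has 4% to 32% more variance than the adjusted analysis for r between 0.3 and 0.9, worth 0.4 to 7.2 points of power at 0.3 SD. These figures rest on equal SDs, a common correlation, 58/29 evaluable subjects and an assumed effect, none of which the documents give for this questionnaire. The change is worth making but modest: the t-tests remain valid, and the primary endpoint, success criterion, sample size and interim are untouched.

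**What to change.** In Section 10.6.4, or in the formal analysis plan before unmasking:

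- Name as the main between-arm VFQ-25 analysis a linear model with Week 12 change in total score as response, baseline total score as covariate and treatment as factor, on observed data as already planned.
- Analyse subscales the same way, as supportive.
- Keep the two-sample and within-arm t-tests and the Wilcoxon tests as supportive, and report item scores as summaries.

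This takes one or two sentences, needs no new data and uses the same type of model as BCVA. It costs one degree of freedom, about 1.2% of variance at 87 subjects. A subject with a Week 12 score but no baseline score would drop out of the main model, though not out of the supportive t-test on the score.
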